9.3. Primary Safety Endpoint

Device related adverse events (AEs)

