Study Design	A single-center, prospective, single arm study to evaluate the performance related to the use of the ARES during bronchoscopic procedures. The Auris system will be used in conjunction with a navigational bronchoscopy procedure.
Number of Patients	The study will enroll up to 60 patients. It is expected that enrollment will take up to 6 months.

Sites		
Duration of Study	Each enrolled subject will be followed up to 6 weeks (± 7 days) post procedure.	
Primary Effectiveness Endpoint	The primary effectiveness endpoint is the completion of the intended bronchoscopic procedure with the ARES, as defined by the ability to acquire tissue with biopsy tools.	
Secondary Effectiveness Endpoints	 The following will be considered secondary endpoints: Identification of correct bronchi leading to the targeted lesions Ability to localize targeted lesion Alignment capabilities Time to REBUS confirmation (lesion localization), time to the tissue acquisition confirmation, Total procedure time (from introduction to removal of the bronchoscope) and procedure interruptions Diagnostic yield Conversion to conventional bronchoscopic procedure Anesthesia time 	
Primary Safety Endpoint	Device or procedure related adverse events (AEs).	
Secondary Safety Endpoint	Complications unrelated to device.	
Follow-Up Schedule	Each enrolled subject will be followed up to 6 weeks ±7 days post procedure.	

CONFIDENTIAL

Pre-Operative Inclusion Criteria	 1. 18 to 80 years of age; 2. Capable and willing to give informed consent; 3. Acceptable candidate for an elective, non-emergent bronchoscopic procedure; 4. Solid peripheral lung lesions suspected of malignancy, between 1.5-7cm in size identified on thin slice CT scan with 30 days of the intended bronchoscopy 	
Pre-Operative Exclusion Criteria	 Subjects will be excluded from participating in this Study if they meet any of the following criteria prior to initiation of the endoscopic procedure: Medical contraindication to bronchoscopy; Ground glass opacity lesions on pre-procedure CT Participation in any other clinical trial 30 days before and throughout the duration of the study; Uncontrolled or irreversible coagulopathy; Female subjects who are pregnant or nursing or those of child-bearing potential refusing a pregnancy test; CT scan done over a month before the bronchoscopy procedure. 	

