8.5. Post Bronchoscopy

Prior to hospital discharge, all subjects will be evaluated for adverse events. These data will be captured in the Case Report Forms. The patient will be managed post-operative in a dedicated post-procedure area as per standard practices at El Camino Hospital. The subject will be monitored for postoperative symptoms and will undergo a chest X-ray within 2 hours from the conclusion of the procedure, to rule out complications such as pneumothorax. Prior to hospital discharge, the investigator and/or designee will arrange a follow-up appointment.

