14.1. General

All adverse events (AE) and serious adverse events (SAE) will be monitored from the time of enrollment through the end of follow-up.

An AE is defined as any undesirable clinical occurrence in a patient whether or not it is considered to be device related. In addition, the definition of AE applies to any event with an onset post study procedure or to any underlying diseases, present at baseline, that exacerbate in severity post study procedure. Therefore, an underlying disease that was present at the time of enrollment is not reported as an AE, but any increase in the severity of the underlying disease is to be reported as an AE. All reported AEs must be recorded in the database. A description of the event, including the start date, resolution date, action taken, and the outcome should be provided, along with the Investigator's assessment of the relationship between the AE, the study treatment and the study procedure.

The following definitions for rating severity of adverse events will be used:

- Mild: Awareness of signs or symptoms, but easily tolerated; are of minor irritant type; causing no loss of time from normal activities; symptoms would not require medication or a medical evaluation; signs or symptoms are transient.
- Moderate: Interferes with the subject's usual activity and/or requires symptomatic treatment.
- Severe: Symptom(s) causing severe discomfort and significant impact of the subject's usual activity and requires treatment.

A serious adverse event (SAE) is defined as an event which leads to:

- Death due to any cause
- Life-threatening condition
- Results in persistent or significant disability/incapacity
- Requires in-patient hospitalization or prolonged hospitalization
- Necessitates an intervention to prevent a permanent impairment of a body function or permanent damage to a body structure
- Results in congenital abnormality

All SAE's will be reported.

Device-Related Adverse Event: an adverse event is considered to be device-related when, in the judgment of the Investigator, the clinical event has a reasonable time sequence associated with use of the AURIS ROBOTIC ENDOSCOPY SYSTEM (ARES) and is unlikely to be attributed to concurrent disease or other procedures or medications. It is reasonable to believe that the system directly caused or contributed to the adverse event.

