Procedure-Related Adverse Event: an adverse event is considered to be procedure-related when, in the judgment of the Investigator; it is reasonable to believe that the event is associated with the assigned study procedure and is not specific to the **AURIS ROBOTIC ENDOSCOPY SYSTEM (ARES)** used. Other products, surgical techniques, or medications required specifically for the procedure are likely to have contributed to the occurrence of the event.

Concomitant Medication-Related Adverse Event: an adverse event is considered to be concomitant medication related when, in the judgment of the Investigator, it is reasonable to believe that the event is associated with concomitant medications used in conjunction with the **AURIS ROBOTIC ENDOSCOPY SYSTEM (ARES)** and is not otherwise specific to the **AURIS ROBOTIC ENDOSCOPY SYSTEM (ARES)** (e.g. bleeding associated with anticoagulation medication).

Pre-Existing Condition-Related Adverse Event: an adverse event is considered to be related to a pre-existing condition when, in the judgment of the Investigator, it is reasonable to believe that the event is associated with the subject's pre-existing condition and is not specific to the AURIS ROBOTIC ENDOSCOPY SYSTEM (ARES) or procedure. Pre-existing conditions that are aggravated or become more severe during or after the procedure should be evaluated on a case-by-case basis to

determine if the event may be more appropriately classified as device-related or procedure-related.

Auris Surgical Robotics, Inc., or its designee, in cooperation with the Investigator, will assess all adverse events considered to be device-related for potential reportability to the FDA and other regulatory authorities as an Unanticipated Adverse Device Effect (UADE).

The Investigator should follow all unresolved serious adverse events until the events are resolved, the subject is lost to follow-up, the subject has withdrawn consent, or the adverse event is otherwise explained.

For purposes of this study, the following events are not likely to be device-specific adverse events, because they are typical procedure/anesthesia related adverse events normally expected to occur in conjunction with these types of bronchoscopic procedures / post-procedure, or are associated with customary, standard care of subjects undergoing these procedures:

- Any pre-planned surgical procedures
- Bleeding
- Pneumothorax
- Post-procedure respiratory insufficiency

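### The synopsis and Section 9.3 define the primary safety endpoint differently, and the end of Section 14.1 conflicts with the recording rule for some non-serious events

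*Protocol*

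**What the plan says.** **Primary safety endpoint.** The protocol synopsis gives "Device or procedure related adverse events (AEs". Section 9.3 gives "Device related adverse events (AEs". Nothing states which prevails.

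**Secondary safety endpoint.** The synopsis and Section 9.4 use the same words: "Complications unrelated to device".

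**Attribution categories.** Section 14.1 calls an event device-related when, among other conditions, "It is reasonable to believe that the system directly caused or contributed to the adverse event". It calls an event procedure-related when "it is reasonable to believe that the event is associated with the assigned study procedure and is not specific to the" ARES. Section 14.2.1 has the relationship to device and to procedure recorded for each event on the Adverse Event CRF.

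**Listed events.** Section 14.1 also states that "the following events are not likely to be device-specific adverse events, because they are typical procedure/anesthesia related adverse events" and lists bleeding, pneumothorax and post-procedure respiratory insufficiency. The closing paragraph of 14.1 calls the list guidance and leaves it to the investigator's judgement whether these events are reported as adverse events. The first item on the list, "Any pre-planned surgical procedures", is not part of this point.

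**The concern.** A primary endpoint needs one definition. Here the words that the synopsis has and Section 9.3 lacks name a category that the protocol defines on its own terms, so the difference is more than shorthand. It also affects the complications the protocol itself expects, because 14.1 steers bleeding, pneumothorax and respiratory insufficiency away from the device category.

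Two things are at stake. First, the same recorded data give two primary safety results, and whoever writes the report could choose between them with the data in view. Second, and smaller, a non-serious event that an investigator decides not to report as an adverse event could be missing from either result.

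**Working it through.** No sample-size or power figure bears on this point, so the check is a comparison of text.

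**Step 1: classify events under each version.** Divide the recorded adverse events by the 14.1 definitions. Let D be the number judged device-related, P the number judged procedure-related and not device-related, and N the number related to neither.

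| Event judged | Synopsis primary | Section 9.3 primary | Secondary (synopsis and 9.4) |
|---|---|---|---|
| Device-related (D) | counts | counts | does not count |
| Procedure-related, not device-related (P) | counts | does not count | counts, if a complication |
| Neither (N) | does not count | does not count | counts, if a complication |

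**Step 2: compare the primary counts.** The synopsis count is D + P and the 9.3 count is D, so the difference is (D + P) − D = P. The versions agree only if no event is judged procedure-related without being device-related.

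**Step 3: check for overlap with the secondary endpoint.** Under 9.3 with 9.4, no event is in both endpoints. Under the synopsis, every complication in P is in both, because the secondary wording excludes only device-related events.

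**Step 4: apply this to one event.** Section 8.5 schedules a chest X-ray "to rule out complications such as pneumothorax", so the protocol treats pneumothorax as a complication. A pneumothorax judged procedure-related and not device-specific is primary and secondary under the synopsis, and secondary only under 9.3 with 9.4.

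**Step 5: check the recording rules for the listed events.**
- The adverse event definition in 14.1 covers any undesirable clinical occurrence, device-related or not.
- The list in 14.1 itself describes these events as typical procedure or anesthesia related adverse events.
- Section 14.2.1, whose heading covers serious and non-serious events, makes entry on the Adverse Event CRF mandatory for potentially procedure-related events.
- The closing paragraph of 14.1 makes reporting the listed events as adverse events a matter of the investigator's judgement.
- Section 14.1 requires all serious adverse events to be reported, so the conflict is confined to non-serious events.

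A non-serious pneumothorax judged procedure-related must therefore be recorded under 14.2.1, yet may go unreported under the end of 14.1.

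**The case against.** **The endpoint drives no decision.** The study has no formal hypothesis, no statistical size or power, and no threshold or stopping rule based on this endpoint. Relatedness to device and procedure is recorded, so both counts come from the same data. For recorded events, what moves is the primary or secondary label in a descriptive single-arm feasibility study. This stands, and it limits the seriousness of the point. It does not settle which count is the headline.

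**A device-only endpoint is reasonable.** The study objective is device performance, and 9.3 with 9.4 already separates events cleanly. This also stands. The fault is that two definitions coexist; neither one is wrong in itself.

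**The 14.1 list may concern attribution only.** It is introduced as a statement about what is device-specific, and the closing paragraph calls it guidance. On that reading the investigator's discretion is to override the suggested attribution. That may be the intent, but the words concern whether the events are reported as adverse events at all. It can also be argued that 14.2.1 binds only events that are both serious and related. The section heading, and the and/or wording of the reporting rule in Section 20.3, weigh against this.

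**Other controls capture these events.** All subjects are evaluated for adverse events before discharge and have a chest X-ray within 2 hours (8.5). Adverse events are recorded at follow-up (8.3), incoming data are monitored (11) and CRFs are checked against source (12.1). These reduce the risk of under-recording but do not remove it, since a monitor could accept an unreported event as a permitted judgement.

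**Stronger readings that the documents do not support.** A reader might multiply the risk bands in 1.2.1 by the 60 patients to size the shift. Those bands expressly exclude biopsy, which is part of the study procedure. The sum would come mostly from cough, wheeze and shortness of breath. Treating all of it as the shift would also assume that every event is attributed to the procedure and none to the device. A reader might also take the 25% pneumothorax rate for transthoracic needle aspiration in 1.1 as the study's safety comparator. That figure supports the non-significant-risk classification only; no endpoint or analysis is compared with it.

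**Conclusion.** The inconsistency is real and should be fixed, but it does not undermine the study. The synopsis and 9.3 define different primary safety endpoints, and the counts differ by exactly the number of adverse events judged procedure-related and not device-related. That number cannot be estimated from the protocol. The consequence is an ambiguous headline safety result, open to choice after the data are seen.

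The recording conflict at the end of 14.1 is a minor, separate point. It concerns non-serious bleeding, pneumothorax and post-procedure respiratory insufficiency only. Some under-recording is possible; the documents do not show that it is likely.

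The conclusion assumes that the 14.1 definitions govern the endpoint terms, and that complications in the secondary endpoint include pneumothorax, as 8.5 implies.

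**What to change.** Before results are seen, state one primary safety definition in both the synopsis and Section 9.3. The sponsor has two workable options:

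- **(a) Device or procedure related events.** This matches the grouping in the 14.2.1 recording rule. The secondary endpoint must then change in both the synopsis and 9.4 to events related to neither device nor procedure.
- **(b) Device-related events only.** This needs an edit only to the primary endpoint in the synopsis, because 9.3 and 9.4 already do not overlap.

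In either case, report device-related and procedure-related counts separately.

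As a minor change, reconcile the closing paragraph of 14.1 with the adverse event definition and with 14.2.1. Bleeding, pneumothorax and post-procedure respiratory insufficiency should be recorded on the Adverse Event CRF with severity and relatedness when they occur, and the investigator's discretion should cover attribution only. Discretion may remain for pre-planned surgical procedures.

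The cost is protocol wording: adverse events, relatedness and the post-procedure chest X-ray are already collected. The one downside is that the reported primary safety count may be higher under option (a).

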9.4. Secondary Safety Endpoint

Complications unrelated to device.

10.Statistical Considerations

None

11.Data Management – Data Collection and Processing

Standardized CRFs will be utilized by participating site using a standardized database. Conventional paper-based CRFs will be used and send to a sponsor designee via secure encrypted emails. Investigator is responsible for the accurate completion and timely submission of the data collected during the Study. Incoming data will be monitored by the sponsor or designee to identify inconsistent or missing data and any adverse events. Any data issues are to be promptly addressed with the investigator. Quality assurance procedures will be established to ensure that complete, accurate and timely data are submitted, that protocol requirements are followed and that complications, adverse events and adverse device effects are correctly reported and investigated, as appropriate. Investigator is to maintain all source documents as required by the protocol, including laboratory results, supporting medical records, and signed Informed Consent forms. The source documents will be used during the regular monitoring visits to verify information from the database against data contained on the completed CRFs.

The Principal Investigator must maintain detailed records on all subjects who sign the Informed Consent and begin the pre-procedure evaluation. Data for enrolled subjects will be entered into CRFs provided by the Sponsor. All data should be entered completely, promptly and legibly. For source documents, corrections should be made in a manner that does not obscure or eliminate the original error, by striking through the original data with one line, and initialing and dating the change, along with the reason for the change (if not obvious).

Study Exit CRFs are completed for all enrolled subjects, regardless if they did or did not complete the Study (e.g., subject discontinuation, Study termination).

12.Monitoring Procedures

12.1. Monitoring

Monitoring visits to the clinical sites will be made periodically during the study by the Sponsor's designee to ensure that all aspects of the current, approved protocol/amendment(s) are followed. Original source documents will be reviewed for verification of data in the database. The Investigator/institution guarantees direct access to

original source documents by Auris Surgical Robotics, Inc. personnel, their designees, and appropriate regulatory authorities. In the event that the original medical records cannot be obtained for a patient that is seen by a non-study physician at a non-study institution, photocopies of the original source documents must be made available for review.

It is important that the Investigator and relevant study personnel are available during the monitoring visits and that sufficient time is devoted to the process.

Phone contacts and site visits will be conducted to ensure that the protocol is being followed and that any protocol deviations are properly documented. Clinical monitoring will include a verification that Informed Consent was properly obtained for all enrolled study participants, a review of clinical records for accuracy and completeness, resolution of missing or inconsistent results and a review of source documents. The clinical monitor will verify that the Case Report Forms (CRFs) are in agreement with the source documentation and other records. The investigator will make available to the clinical monitor for review all Informed Consent documents, source documentation, original laboratory data and other relevant records for all enrolled subjects at the site. It is important that the investigator and other relevant site personnel are available for consultation with the clinical monitors during the monitoring visits and that sufficient time is devoted at the site to the monitoring process.

Additionally, telephone and/or e-mail contact will be conducted on a regular basis with the investigator and the site staff to ensure that the protocol is being followed and to address any issues that may occur during the course of the Study.

If a deficiency is noted during an on-site visit (or at any other time during the course of the Study), the clinical monitor is required to discuss the situation with the investigator and the Sponsor (if required) to secure compliance.

12.2. Device Distribution and Accountability

12.2.1. Device Distribution

Auris Robotic Endoscopy System (ARES) for Bronchoscopy will be provided free of charge to the investigator for his exclusive use in this NSR study.

12.2.2. Device Accountability

Auris Surgical Robotics will maintain device accountability as required for this NSR Study.

12.2.3. Return of Materials Upon Study Termination

The Auris Robotic Endoscopy System (ARES) for Bronchoscopy will be returned at the end of the study.

13. Quality Control and Quality Assurance

13.1. Site Training

To ensure accurate, complete, and reliable data, the Sponsor or its representatives will provide instructional material to the Study sites, as appropriate;

- Instruct the Investigators and Study personnel on the protocol, the completion of the CRFs, and Study procedures
- Communicate regularly with site personnel via mail, email, telephone, and/or fax
- Make periodic visits to the Study sites.

During those visits, the sponsor's designee will monitor the subject data recorded in the CRFs against source documents at the Study site.

13.2. Physician Training

Prior to enrolling subjects in the Study, investigators will be provided didactic training on the procedural steps required to use the ARES system. Physicians who have not previously used the device will receive training with a Sponsor-designated proctor using a benchtop model to simulate the use of the ARES system.

13.3. Audits and Inspections

The Principal Investigator for the site will inform the Sponsor or the Sponsor's designee in advance if they are to be audited or inspected by any regulatory agencies. The Sponsor or the Sponsor's designee will also inform the site if they are made aware of a pending audit or inspection by a regulatory agency. No FDA inspections are expected to be associated with this NSR Study.

14.Adverse Events

14.1. General

All adverse events (AE) and serious adverse events (SAE) will be monitored from the time of enrollment through the end of follow-up.

An AE is defined as any undesirable clinical occurrence in a patient whether or not it is considered to be device related. In addition, the definition of AE applies to any event with an onset post study procedure or to any underlying diseases, present at baseline, that exacerbate in severity post study procedure. Therefore, an underlying disease that was present at the time of enrollment is not reported as an AE, but any increase in the severity of the underlying disease is to be reported as an AE. All reported AEs must be recorded in the database. A description of the event, including the start date, resolution date, action taken, and the outcome should be provided, along with the Investigator's assessment of the relationship between the AE, the study treatment and the study procedure.

The following definitions for rating severity of adverse events will be used:

- Mild: Awareness of signs or symptoms, but easily tolerated; are of minor irritant type; causing no loss of time from normal activities; symptoms would not require medication or a medical evaluation; signs or symptoms are transient.
- Moderate: Interferes with the subject's usual activity and/or requires symptomatic treatment.
- Severe: Symptom(s) causing severe discomfort and significant impact of the subject's usual activity and requires treatment.

A serious adverse event (SAE) is defined as an event which leads to:

- Death due to any cause
- Life-threatening condition
- Results in persistent or significant disability/incapacity
- Requires in-patient hospitalization or prolonged hospitalization
- Necessitates an intervention to prevent a permanent impairment of a body function or permanent damage to a body structure
- Results in congenital abnormality

All SAE's will be reported.

Device-Related Adverse Event: an adverse event is considered to be device-related when, in the judgment of the Investigator, the clinical event has a reasonable time sequence associated with use of the AURIS ROBOTIC ENDOSCOPY SYSTEM (ARES) and is unlikely to be attributed to concurrent disease or other procedures or medications. It is reasonable to believe that the system directly caused or contributed to the adverse event.

Procedure-Related Adverse Event: an adverse event is considered to be procedure-related when, in the judgment of the Investigator; it is reasonable to believe that the event is associated with the assigned study procedure and is not specific to the **AURIS ROBOTIC ENDOSCOPY SYSTEM (ARES)** used. Other products, surgical techniques, or medications required specifically for the procedure are likely to have contributed to the occurrence of the event.

Concomitant Medication-Related Adverse Event: an adverse event is considered to be concomitant medication related when, in the judgment of the Investigator, it is reasonable to believe that the event is associated with concomitant medications used in conjunction with the **AURIS ROBOTIC ENDOSCOPY SYSTEM (ARES)** and is not otherwise specific to the **AURIS ROBOTIC ENDOSCOPY SYSTEM (ARES)** (e.g. bleeding associated with anticoagulation medication).

Pre-Existing Condition-Related Adverse Event: an adverse event is considered to be related to a pre-existing condition when, in the judgment of the Investigator, it is reasonable to believe that the event is associated with the subject's pre-existing condition and is not specific to the AURIS ROBOTIC ENDOSCOPY SYSTEM (ARES) or procedure. Pre-existing conditions that are aggravated or become more severe during or after the procedure should be evaluated on a case-by-case basis to

determine if the event may be more appropriately classified as device-related or procedure-related.

Auris Surgical Robotics, Inc., or its designee, in cooperation with the Investigator, will assess all adverse events considered to be device-related for potential reportability to the FDA and other regulatory authorities as an Unanticipated Adverse Device Effect (UADE).

The Investigator should follow all unresolved serious adverse events until the events are resolved, the subject is lost to follow-up, the subject has withdrawn consent, or the adverse event is otherwise explained.

For purposes of this study, the following events are not likely to be device-specific adverse events, because they are typical procedure/anesthesia related adverse events normally expected to occur in conjunction with these types of bronchoscopic procedures / post-procedure, or are associated with customary, standard care of subjects undergoing these procedures:

- Any pre-planned surgical procedures
- Bleeding
- Pneumothorax
- Post-procedure respiratory insufficiency

This listing of events is intended to provide guidance to the investigational sites for purposes of adverse event reporting. The Investigator at the investigational site should utilize his/her own clinical judgment in evaluating adverse experiences, and may decide that the above events should be reported as adverse events.

